8.2.3. Special Reporting Situations

When a report contains a Janssen product, an identifiable patient, and identifiable reporter, the following events represent Special Reporting Situations:

- Drug exposure during pregnancy (maternal and paternal)
- overdose of a Janssen medicinal product
- pregnancy exposure (maternal and paternal)
- exposure to a Janssen medicinal product from breastfeeding
- suspected abuse/misuse of a medicinal Janssen product
- · inadvertent or accidental exposure to a medicinal Janssen medicinal product
- any failure of expected pharmacological action (i.e., lack of effect) of a Janssen medicinal product
- unexpected therapeutic or clinical benefit from use of a Janssen medicinal product
- medication error involving a Janssen product (with or without patient exposure to the medicinal Johnson & Johnson product, e.g., name confusion)
- suspected transmission of any infectious agent via a medicinal product.

These safety events may not meet the definition of an adverse event; however, from Janssen Scientific Affairs, LLC perspective, they are treated in the same manner as adverse events. Special situations should be recorded on the Adverse Event page of the Department of Urology database.

Any special situation that meets the criteria of a serious adverse event should be recorded on a Serious Adverse Event Report Form and be reported to Janssen Scientific Affairs, LLC within 24 hours of becoming aware of the event.

8.2.4. Adverse Events Reporting

All Adverse Events

General guidelines – Toxicity will be scored using CTC AE Version 4.0 for toxicity and adverse event reporting. A copy of the CTCAE Version 4.0 can be downloaded from the CTEP homepage (http://ctep.info.nih.gov). All appropriate treatment areas should have access to a copy of the CTC AE Version 4.0. All adverse clinical experiences must be recorded according to the table "Recommended Adverse Events Recording Guidelines", after they were documented in the treating

2015-0693 June 10, 2022 Page 31

physician's clinic note, utilizing the NCI CTC v 4.0 to determine terminology and grade. Adverse events will be recorded following the first exposure to study drug until 30 days following the last administration of study treatment or study discontinuation/termination, whichever is earlier. For discontinued patients, follow up on serious adverse events will be conducted up to 30 days from last treatment of study drug.

When an adverse event occurs, the following information and assessments should be recorded:

- i) The signs, symptoms, or diagnosis of the event.
- ii) The date of the event.
- iii) The adverse event severity, using the criteria outlined above.
- iv) The relationship of the event to the study drug as outlined above.
- v) The description of any action taken regarding study drug disposition.
- vi) Any required therapy, medication, treatment, or diagnostic procedure.

The Principal Investigator (PI) or physician designee is responsible for the appropriate medical management of all adverse events. The PI or physician designee must evaluate each adverse experience for its seriousness and determine attribution to study drug.

The investigator must appraise all abnormal laboratory results for their clinical significance. If any abnormal laboratory result is considered clinically significant, the investigator must provide details about the action taken with respect to the test drug and about the patient's outcome.

The investigator must appraise all evaluation test results for their clinical significance. If any abnormal evaluation test result is considered clinically significant, the investigator must provide details about the action taken with respect to the test drug and about the patient's outcome. Any evaluation test that is not considered clinically significant will not be captured as an adverse event (AE).

Serious Adverse Events

All events occurring during the conduct of a protocol and meeting the definition of a SAE must be reported to the IRB in accordance with the timeframes and procedures outlined in "The University of Texas M. D. Anderson Cancer Center Institutional Review Board Policy for Investigators on Reporting Unanticipated Adverse Events for Drugs and Devices". Unless stated otherwise in the protocol, all SAEs, expected or unexpected, must be reported to the IND Office, regardless of attribution (within 5 working days of knowledge of the event).

All life-threatening or fatal events, that are unexpected, and related to the study drug, must have a written report submitted within **24 hours** (next working day) of knowledge of the event to the Safety Project Manager in the IND Office.

Unless otherwise noted, the electronic SAE application (eSAE) will be utilized for safety reporting to the IND Office and MDACC IRB.

Serious adverse events will be captured from the time of the first protocol-specific intervention, until 30 days after the last dose of drug, unless the participant withdraws consent. Serious adverse events must be followed until clinical recovery is complete and laboratory tests have returned to baseline, progression of the event has stabilized, or there has been acceptable resolution of the event. Additionally, any serious adverse events that occur after the 30 day time period that are related to the study treatment must be reported to the IND Office. This may include the development of a secondary malignancy.

Reporting to FDA:

Serious adverse events will be forwarded to FDA by the IND Sponsor (Safety Project Manager IND Office) according to 21 CFR 312.32.

It is the responsibility of the PI and the research team to ensure serious adverse events are reported according to the Code of Federal Regulations, Good Clinical Practices, the protocol guidelines, the sponsor's guidelines, and Institutional Review Board policy.

Maintenance of Safety Information:

Safety information will be maintained in a clinical database/repository in a retrievable format. At a minimum, at the end of the treatment phase (="last patient off treatment") as well as the end of the follow-up phase (="last patient out") of the Study, the Principal Investigator shall provide all adverse events, both serious and non-serious, in report format. However, in certain circumstances more frequent review of the safety data may be necessary, e/g/ to fulfill a regulatory request, and as such the data shall be made available within a reasonable timeframe at Janssen Scientific Affairs' request.

Individual Case Safety Report (ICSR)

A valid ICSR must contain the four minimum criteria required to meet regulatory reporting requirements.

- an identifiable subject (but not disclosing personal information such as the subject's name, initials or address)
- an identifiable reporter (investigational site)
- a Janssen medicinal product
- an adverse event, outcome, or certain special situations

The minimum information required is:

- suspected Janssen medicinal product (doses, indication)
- date of therapy (start and end date, if available)
- batch or lot number, if available
- subject details (subject ID and country)
- gender
- age at AE onset
- reporter ID
- adverse event detail (AE verbatim in English), onset date, relatedness, causality, action taken, outcome, (if available)
- Janssen protocol ID

Product Quality Complaint (PQC)

A product quality compliant is defined as any suspicion of a product defect related to a potential quality issue during manufacturing, packaging, release testing, stability monitoring, dose preparation, storage or distribution of the product, or delivery system. Not all PQCs involve a subject. Lot and batch numbers are of high significance and need to be collected whenever available.

Examples of PQC include but not limited to:

- Functional Problem: e.g., altered delivery rate in a controlled release product
- Physical Defect: e.g. abnormal odor, broken or crushed tablets/capsules
- Potential Dosing Device Malfunction: e.g., autoinjector button not working, needle detaching from syringe
- Suspected Contamination
- Suspected Counterfeit

Procedures for Reporting Safety Data and Product Quality Complaints (PQCs) for Janssen Medicinal Products to Janssen Scientific Affairs, LLC

All adverse events and special situations, whether serious or non-serious, related or not related, following exposure to a Janssen medicinal product are to be documented by the investigator and recorded in the Department of Urology database and in the subject's source records. Investigators must record in the

2015-0693 June 10, 2022 Page 34

Department of Urology database (REDCap) their opinion concerning the relationship of the adverse event to a Janssen medicinal product.

All (serious and non-serious) adverse events reported for a Janssen medicinal product should be followed-up in accordance with clinical practice.

SAEs and Special Reporting Situations

All serious adverse events that have not resolved by the end of the study, or that have not resolved upon discontinuation of the subject's participation in the study, must be followed until any of the following occurs:

- The event resolves
- The event stabilizes
- The event returns to baseline, if a baseline value/status is available
- The event can be attributed to agents other than the study drug or to factors unrelated to study conduct
- It becomes unlikely that any additional information can be obtained (subject or health care practitioner refusal to provide additional information, lost to followup after demonstration of due diligence with follow-up efforts)

The PRINCIPAL INVESTIGATOR will transmit all SAEs and special situations following exposure to a Janssen product under study in a form provided by Janssen Scientific Affairs, LLC in accordance with an acceptable transmission method, in English within 24-hours of becoming aware of the event(s).

All follow-up information for serious adverse events that are not resolved at the end of the study or by the time of patient withdrawal must be reported directly by the PRINCIPAL INVESTIGATOR, within 24 hours becoming aware, to Janssen Scientific Affairs, LLC using the Janssen/MedWatch 's Serious Adverse Event Form

All available clinical information relevant to the evaluation of a related SAE, serious ADR or special situation is required.

- The PRINCIPAL INVESTIGATOR is responsible for ensuring that these
 cases are complete and if not are promptly followed-up. A safety report is not
 considered complete until all clinical details needed to interpret the case are
 received. Reporting of follow-up information should follow the same timeline
 as initial reports.
- Copies of any and all relevant correspondences with regulatory authorities and ethics committees regarding any and all serious adverse events, irrespective of association with the Janssen Product under study, are to be provided to Janssen Scientific Affairs, LLC using an acceptable transmission

method within 24 hours of such report or correspondence being sent to applicable health authorities.

PQC Reporting

A PQC may have an impact on the safety and efficacy of the product. Timely, accurate, and complete reporting and analysis of PQC information from studies are crucial for the protection of patients, investigators, and Janssen Scientific Affairs, LLC, and are mandated by regulatory agencies worldwide. Janssen Scientific Affairs, LLC has established procedures in conformity with regulatory requirements worldwide to ensure appropriate reporting of PQC information. Lot and/or Batch #s shall be collected or any reports failure of expected pharmacological action (i.e., lack of effect). The product should be quarantined immediately and if possible, take a picture.

All initial PQCs involving a Janssen medicinal product under study must be reported to Janssen Scientific Affairs, LLC by the PRINCIPAL INVESTIGATOR within 24 hours after being made aware of the event. The Janssen contact will provide additional information/form to be completed.

If the defect for a Janssen medicinal product under study is combined with either a serious adverse event or non-serious adverse event, the PRINCIPAL INVESTIGATOR must report the PQC to Janssen Scientific Affairs, LLC according to the serious adverse event reporting timelines. A sample of the suspected product should be maintained for further investigation if requested by Janssen Scientific Affairs, LLC.

Pregnancy

All initial reports of pregnancy must be reported to Janssen Scientific Affairs by the study-site personnel within 24 hours of their knowledge of the event. Abnormal pregnancy outcomes (eg, spontaneous abortion, stillbirth, and congenital anomaly) are considered serious adverse events and must be reported as a Serious Adverse Event.

Because the effect of the study drug on sperm is unknown, pregnancies in partners of male subjects included in the study will be reported by the study-site personnel within 24 hours of their knowledge of the event.

Follow-up information regarding the outcome of the pregnancy and any postnatal sequelae in the infant will be required.

Transmission Methods

2015-0693 June 10, 2022 Page 36

The following methods are acceptable for transmission of safety information to Janssen Scientific Affairs. LLC:

 Electronically via Janssen SECURE Email service (preferred) - [contact]

Please use the contact information and process information provided by Janssen.

Abnormal Laboratory Results

The criteria for determining whether an abnormal laboratory test result should be reported as an adverse event are as follows:

- 1. Test result is associated with accompanying symptoms, and/or
- 2. Test result requires additional diagnostic testing or medical/surgical intervention (merely repeating an abnormal test, in the absence of any of the above conditions, does not meet criteria for reporting and an AE), and/or
- 3. Test result leads to a change in study dosing or death from the study, significant additional concomitant drug treatment or other therapy, and/or
- 4. Test result leads to any of the outcomes included in the definition of a serious adverse event, and/or
- 5. Test result is considered to be an adverse event by the investigator

Any abnormal test result that is determined to be an error does not require reporting as an adverse event, even if it did meet one of the above conditions except for condition #4. Clinically significant laboratory results must be recorded in the Department of Urology database.

Dose Modification/Toxicity Management

Subjects who experience a Grade 3 or greater toxicity considered to be related to apalutamide that cannot be ameliorated by the use of adequate medical intervention should have their treatment interrupted until the toxicity improves to a Grade 1 or baseline. Subjects may subsequently be re-started on study drug at a reduced dose follow a discussion between the Principal Investigator. Dose modifications are provided as guidance and should not replace the investigator's own clinical judgment.

[figure not shown]
Toxicity	Dose of JNJ-56021927 (assuming 240 mg/day dosing)
Grade 1 or 2	If a Grade 2 Toxicity has not resolved to Grade≤1 after 30 days, study drug will be discontinued. For all other Grade 1 or 2 Toxicities there will be no change.
(First Occurence) ≥Grade 3	Hold until Grade 1 or baseline, resume at full dose
First Recurrence ≥Grade 3	Hold until Grade 1 or baseline, resume at 180 mg (3 tablets)
Second Recurrence ≥Grade 3	Hold until Grade 1 or baseline, resume at 120 mg (2 tablets)
Third Recurrence ≥Grade 3	Discontinue
First occurrence of seizure of any grade or Grade 4 neurotoxicity	Discontinue

Rash

Dose modifications for rash are allowed only for apalutamide and are summarized in below table. If the skin rash has any component of desquamation, mucosal involvement, or pustules, stop dosing with apalutamide, refer to dermatologist for evaluation, and a skin biopsy is recommended (in addition to the interventions listed in below Table) If the skin rash is Grade 3 or higher, asking the subject to consent to documentation by a photograph and further evaluation by a dermatologist should also be considered.

Severity	Intervention
Grade 1	 Continue apalutamide at current dose Initiate dermatological treatment^a Topical steroid cream AND Oral Antihistamines Monitor for change in severity^a
Grade 2 (or symptomatic Grade 1) ^b	 Hold apalutamide for up to 28 days Initiate dermatological treatment^a Topical steroid cream AND Oral Antihistamines Monitor for change in severity^a If rash or related symptoms improve, reinitiate apalutamide when rash is Grade≤1. Consider dose reduction at a 1 dose level reduction^c.
Grade ≥3 ^d	 Hold apalutamide for up to 28 days Initiate dermatological treatment^a Topical steroid cream AND Oral Antihistamines AND Consider short course of oral steroids Reassess after 2 weeks (by site staff), and if the rash is the same or has worsened, initiate oral steroids (if not already done) and refer the subject to a dermatologist Reinitiate apalutamide at a 1 dose level reduction^e when rash is Grade≤1.

2015-0693 June 10, 2022 Page 38

Note: Rash may be graded differently according to the type of rash and associated symptoms. For example, maculo-papular rash is graded by body surface area covered and not severity of the rash. Please consult NCI-CTCAE Version 4.03 for specific grading criteria for other types of rash.

- a Obtain bacterial/viral cultures if infection is suspected
- **b** Subject presents with other rash related symptoms such as pruritus, stinging, or burning
- **c** 1 dose level reduction = 60mg (1 apalutamide tablet)
- **d** If there is blistering or mucosal involvement, stop apalutamide dosing immediately and contact Janssen
- **e** If a subject previously started oral corticosteroids, continue for at least 1 week after resumption of reduced dose of apalutamide. If the proposed total oral steroid use will exceed 28 days, contact Janssen.

Criteria for Discontinuation of Study Treatment

To discontinue Study Treatment, either of the criteria below must be met:

- The patient completed 24 weeks of study treatment;
- Patients who fail to reach a 50% decrease in PSA or demonstrate suspicious changes in DRE at mid-way evaluation (week 9);
- Sustained side effects: patients who have sustained toxicities, such as
 hyperglycemia or hypertension that do not return to NCI CTCAE (version 4.0)
 grade 1 or less within 30 days despite appropriate medical management,
 should be discontinued from the study treatment phase. All end-of-study
 treatment procedures should be conducted. The patient will be followed to the
 pre-op visit;
- Dosing noncompliance: study treatment administration and dosing compliance will be assessed on Day 1 of all cycles, and at Pre-surgery/End of Treatment Visit. A count of study treatment will be conducted during this visit and patient dosing compliance will be assessed. If dosing compliance is not >75% in the absence of toxicity, patient should be re-instructed regarding proper dosing procedures and continue in the protocol. Subsequent dosing compliance procedure will be conducted at each study visit. If a patient misses 14 or more doses within 4 weeks, the patient should be discontinued from the study treatment phase. All end-of-study treatment procedures should be followed. The patient will be followed to the pre-op visit
- Initiation of new anticancer treatment: patients will be discontinued from the study treatment when investigator, in his or her judgment, determines new treatment for prostate cancer is warranted. All end-of-study treatment procedures should be conducted and the patient will be followed to the preoop visit
- Administration of prohibited medications: the patient will be discontinued from the protocol treatment when prohibited drug is administered (Section 8.1.4.3).
 All end-of-study treatment procedures should be conducted and the patient

2015-0693 June 10, 2022 Page 39

will be followed to the pre-op visit. Supportive care medications are permitted with their use following institutional guidelines. The concurrent administration of other anticancer therapy, including cytotoxic, hormonal (except LHRHa), or immunotherapy is prohibited during study treatment phase. Use of other investigational drug therapy for any reason is prohibited

- Patient met Grade 4 criteria for elevated Liver Function Tests or the criteria for dose discontinuation of non-mineralocorticoid based side effects.
- Subjects experiencing toxicity considered to be related to the use of for which more than two dose reductions areneeded will require discontinuation of study drugs.

Withdrawal from Study

An investigator may withdraw a patient from the study at any time based on clinical judgment or if a patient withdraws consent. In this event, the reason(s) for withdrawal must be documented and clarification if withdrawal of consent includes Post-Radical Prostatectomy Evaluation data collection. A patient's decision to take part in the study is voluntary and he may choose not to take part in the study or to stop taking part at any time. If he chooses not to take part or to stop at any time, it will not affect his future medical care or medical benefits. A patient may withdraw from study treatment phase for any reason. In general, subjects who withdraw will not be replaced unless the number of completed subjects falls below the estimated sample size required to provide the desired precision.

Radical Prostatectomy

Within 2 weeks of stopping apalutamide, patients will undergo planned radical prostatectomy. The surgical access is per the attending surgeon discretion such as open or robot-assisted. The extent of primary surgery such as inclusion/exclusion of the neurovascular bundles and bladder neck is per attending surgeon discretion. The seminal vesicles should be completely removed if possible. The lymph node dissection should attempt to consist of an extended template, specifically: a) obturator fossa, b) external iliac from the medial aspect of the external iliac artery and clearing the triangular space at the junction of the external and internal arteries, c) hypogastric artery to include a continuation of the obturator fossa beneath the obturator nerve. The protocol does not require the surgeon to deviate from his/her common practice and judgment in the event unexpected grossly enlarged lymph nodes are encountered.

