3. STUDY OBJECTIVES

3.1. Primary: To determine whether 6 months (24 weeks) of neoadjuvant apalutamide prior to prostatectomy for intermediate risk prostate cancer results in a reduction of aggregate post-operative radiotherapy risk from 35% to 15%.

3.2. Secondary:

- 3.2.1. To determine the safety and tolerability of 6 months (24 weeks) neoadjuvant apalutamide followed by radical prostatectomy for intermediate risk prostate cancer
- 3.2.2. To estimate the frequency of clinical complete responses and "near" complete responses (currently defined as <6mm total tumor volume)
- 3.2.3. To characterize the molecular features of the treated prostate cancers and link them to morphologic characterization
- 3.2.4. To measure the 3-5 year biochemical recurrence rate and quality of life of treated patients as a baseline to inform a larger phase III trial.

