- Concomitant Medications Review
- Adverse Events

Note: At the mid-way evaluation (week 9), patients who fail to reach a 50% decrease in PSA, or demonstrate suspicious changes in DRE will be considered non-responders and recommended for early surgery.

4) Week 12 Procedures (± 3 days):

Optional: Repeat prostate biopsy per urologist's discretion. Acceptable to perform at the week 9 or week 17 visit if requested for patient travel needs.

5) Week 17 Procedures (± 3 days):

- Medication dispensing (neoadjuvant apalutamide)
- Dosing compliance
- Physical exam with DRE if indicated by treating physician
- Vital signs
- ECOG Performance Status
- Laboratories (Serum chemistry and hematology)
- Thyroid Stimulating Hormone (TSH) (T3 and T4 only to be done if TSH is abnormal)
- Prostate-Specific Antigen (PSA) Test and Testosterone
- Concomitant Medications Review
- Adverse Events
- EPIC Quality of Life (QOL) Questionnaire
- Blood collection for Correlative Studies

6) Week 24/ Pre-op/ End of Treatment Visit Procedures (± 3 days):

- Dosing compliance
- Physical exam with DRE
- Vital signs
- ECOG Performance Status
- Laboratories (Serum chemistry and hematology)
- Thyroid Stimulating Hormone (TSH) (T3 and T4 only to be done if TSH is abnormal)
- Prostate-Specific Antigen (PSA) Test and Testosterone
- Concomitant Medications Review
- Adverse Events
- EPIC Quality of Life (QOL) Questionnaire

- Blood collection for Correlative Studies
- 7) Radical Prostatectomy (2 weeks (+/-7 days) after last dose of study drug):
 - Perioperative data collection
 - Pathology Tissue Collection

C. Follow-up Phase:

- 1) Post Radical Prostatectomy: (within 30 days post-op +/- 3 days)
 - Physical exam and DRE if indicated by treating physician
 - Assess complications from surgery at 30 days using Clavien methodology (Table 5).
 - Adverse Events
 - Epic Quality of Life (QOL) Questionnaire
 - PSA, testosterone
- 2) Six Months Post-Radical Prostatectomy: (+/- 4 weeks)
 - a. Update complications to 90 day window
 - b. Use of adjuvant/salvage therapies
 - c. EPIC Quality Of Life (QOL) Questionnaire
 - d. PSA, testosterone
- 3) Twelve Months Post Radical Prostatectomy—Last on-site Study Visit: (+/- 4 weeks)
 - a. EPIC Quality Of Life Questionnaire
 - **b.** PSA, testosterone
 - c. Use of adjuvant/salvage therapies
 - d. Update complications
- 4) Post Study Follow-up Data Collection (on-site or remote): (+/- 4 weeks)
 - **a.** Intervals 24, 36, 48, 60 months

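### The AE and SAE windows in 8.2.4 end 30 days after the last dose, usually before the 30-day post-operative visit at which 7.1 and Table 6 schedule AEs; the rules need reconciling

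*Combined protocol and SAP*

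**What the plan says.** The safety objective (3.2.1) covers the whole sequence of drug and surgery: "To determine the safety and tolerability of 6 months (24 weeks) neoadjuvant apalutamide followed by radical prostatectomy".

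The collection rules are spread over several places:

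- **AE window (8.2.4, All Adverse Events).** Recording starts at first exposure and runs "until 30 days following the last administration of study treatment or study discontinuation/termination, whichever is earlier".
- **SAE window (8.2.4, Serious Adverse Events).** "Serious adverse events will be captured from the time of the first protocol-specific intervention, until 30 days after the last dose of drug", unless consent is withdrawn. Later SAEs must still go to the IND Office if they are related to study treatment.
- **AE schedule (7.1, Follow-up Phase, and Table 6).** Adverse events are an item of the post-operative visit, timed "within 30 days post-op +/- 3 days", and the AE row of Table 6 is marked in the 30-day post-operative column.
- **Surgical complications (7.1 and note g of Table 6).** Graded by Clavien at 30 and 90 days, with updates afterwards.
- **Reporting to the drug supplier (8.2.4).** All adverse events after exposure, serious or not and related or not, are to be documented. No end date is given.
- **Time from last dose to surgery.** Section 7.1 has "Radical Prostatectomy (2 weeks (+/-7 days) after last dose of study drug"). The surgery paragraph at the end of Section 8 has "Within 2 weeks of stopping apalutamide, patients will undergo planned radical prostatectomy", and Section 4 agrees with the latter.
- **Analysis (6.2).** Toxicity is summarised by category, grade and attribution.

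**The concern.** Both windows are anchored to the last dose, while the visit meant to collect post-operative events is anchored to surgery. As surgery follows the last dose by up to three weeks, the windows will usually close before that visit. Site staff then have a schedule telling them to collect adverse events, a window telling them that late ones are out of scope, and a third passage with no limit.

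At stake is the post-operative half of objective 3.2.1. The window decides which post-operative events receive a CTCAE term, a grade and an attribution, and so can enter the 6.2 summary. Because the cut-off moves with the surgery date, the number of post-operative days covered differs from man to man.

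**Working it through.** Count days from the last dose (day 0). Let *s* be the day of surgery.

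- Window closes on day 30 (8.2.4).
- Post-operative day on which it closes = 30 − *s*.
- A visit on post-operative day 30 falls on day *s* + 30, so the gap from closure to visit = (*s* + 30) − 30 = *s* days.
- Share of the 30 post-operative days outside the window = *s*/30.

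| Source of timing | *s* | Window closes, post-op day | Post-op day 30 falls on day | Gap (days) | Share outside |
|---|---|---|---|---|---|
| 7.1, earliest | 7 | 23 | 37 | 7 | 23% |
| 7.1, nominal | 14 | 16 | 44 | 14 | 47% |
| 7.1, latest | 21 | 9 | 51 | 21 | 70% |
| Sections 4 and 8, earliest | 0 | 30 | 30 | 0 | 0% |
| Sections 4 and 8, latest | 14 | 16 | 44 | 14 | 47% |

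With the 3-day tolerance on the visit, the gap under 7.1 runs from 7 − 3 = 4 to 21 + 3 = 24 days. Under the within-2-weeks wording, it vanishes only if surgery is on about the day of the last dose. The visit is worded as falling within 30 days of surgery, so an early visit could land inside the window. The remaining days up to post-operative day 30 would then have no AE visit.

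The plan gives no figure of its own to reproduce here.

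Next, which late events are covered by some other rule:

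- *Surgical complications:* covered by Clavien at 30 and 90 days and beyond. Clavien gives neither a CTCAE grade nor an attribution to study drug.
- *Deaths:* reportable as SAEs whatever the cause (8.2.1).
- *SAEs judged related to treatment:* reportable after day 30 (8.2.4).
- *SAEs judged unrelated:* outside the capture window. Section 8.2.2 classes an event clearly due to another therapeutic intervention as unrelated, so an SAE put down to the operation may fall here.
- *Non-serious AEs not recorded as complications:* outside the AE window, although scheduled at the visit and within the undated supplier wording.

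The last two groups are the residual gap.

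**The case against.** The strongest reply is that the documents show conflicting text and not a demonstrated loss of data, and much of that stands.

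A reader might infer that late post-operative events simply go unrecorded. The plan does not support this. Adverse events are an item of the post-operative visit itself. The supplier paragraph has no end date, and 8.2.4 also asks for a report of all adverse events at the end of follow-up. The SAE section opens by requiring SAEs during the conduct of the protocol to be reported to the IRB, and SAEs to go to the IND Office regardless of attribution. Nor is Clavien confined to technical surgical problems: Grade I in Table 5 takes in any departure from the normal post-operative course, and higher grades include drug treatment and organ dysfunction.

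A reader might also take 70% as the size of the problem. That figure needs surgery on day 21, which the within-2-weeks wording excludes. It is also a share of days, not of events, and the plan gives no data on event timing.

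Finally, the safety analysis is descriptive and single-arm. The toxicity stopping rule in 6.3 counts only events that prevent surgery or treatment-related deaths before it, so neither that rule nor the primary endpoint is touched.

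What remains is that the two explicit windows do cut off before the scheduled visit, and nothing says which rule governs the 6.2 summary. The broader sentences add to the conflict; they do not resolve it.

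**Conclusion.** The point holds as an inconsistency with a limited consequence. The AE and SAE windows conflict with the AE schedule and with the undated supplier wording. At the nominal timing in 7.1, the windows close on post-operative day 16, 14 days before post-operative day 30. The range is 7 to 21 days under 7.1, and 0 to 14 days under Sections 4 and 8.

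The exposed events are CTCAE-graded, attributed AEs not recorded as surgical complications, and SAEs judged unrelated, with onset after the window closes. They may be missed or handled differently between men. Post-operative toxicity in the 6.2 summary may therefore be understated, and its coverage varies with surgery date. It would go too far to say that it is understated: that depends on which rule staff follow and on how many such events occur, and the documents settle neither.

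The day counts assume that the window is counted from the last dose actually taken and that the visit is held at about post-operative day 30.

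**What to change.** - In both the AE and the SAE paragraphs of 8.2.4, end collection at the later of 30 days after the last dose and the 30-day post-operative visit. For men who do not have surgery, end it 30 days after the last dose. Keep the existing rule for later related SAEs.
- Delete the study discontinuation/termination alternative, with its earlier-of condition, from the AE sentence. Do not turn it into a later-of condition: Section 4 keeps men on formal protocol to 12 months, so that could stretch AE recording to the end of study participation. Collection still stops if consent is withdrawn.
- Give the supplier-reporting paragraph of 8.2.4 the same end date.
- Reconcile the two statements of the interval between last dose and surgery (7.1 against Section 4 and the surgery paragraph of Section 8).
- State in 6.2 which post-operative events enter the toxicity summary, and whether by CTCAE or Clavien grade.

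Under the 7.1 timing, collection would run to about day 37, 44 or 51 after the last dose. The visit and its AE review already exist, so the cost is a few lines of text and a few more AE records.
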